**Table 2: Serum markers in obese girls**

	Obese	PCOS	T2D
Number of Participants	19	38	40
ALT (IU/L)	29 $\pm$ 3	38 $\pm$ 3	40 $\pm$ 2
Triglycerides (mg/dl)	78 $\pm$ 8	129 $\pm$ 7	207 $\pm$ 7
HbA1C (%)	5.1 $\pm$ 0.2	5.4 $\pm$ 0.3	7.2 $\pm$ 0.4
2h OSTT glucose >140 mg/dL	20%	50%	100%
HOMA-IR	3.6 $\pm$ 1.3	5.9 $\pm$ 0.4	-

hemoglobin A1c, as an indicator of blood sugar over the previous 3 months and following a (75g glucose +25g fructose) oral sugar tolerance test (OSTT), nearly half of girls had impaired glucose tolerance, defined as a blood glucose  $> 140$  mg/dl at 2 hours.

- Excess hepatic triglyceride is from increased de novo lipogenesis in obese girls with PCOS. In our Resistant and APPLE studies, we examined the differential tissue-specific response to insulin in female youth with PCOS compared to my mentor's ([name]) studies of T2D, utilizing a 4 phase

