### III. Research Methods

#### A. Outcome Measure(s):

Primary Outcome Measure(s): Change in hepatic fat content per treatment type

Secondary Outcome Measure(s): Activity ratios of the hepatic pentose phosphate pathway, TCA cycle and TG synthesis, change in peripheral IR as assessed with an OSTT, measures of sympathetic nervous system activity, hepatic phosphate profile. Indirect measure of DNL (change in TG concentration with OSTT) Targeted glucose and fat metabolism metabolomics, and untargeted exploratory analysis, gut microbiota profile.

Likely contributors to above measures: Lipid/glucose markers:(fasting C-peptide and lipid panel, HbA1c); hepatic markers:(c-reactive protein, glucagon, GLP-1 and leptin at baseline, 5 min and 30 min post glucose load to assess changes with adiponectin, AST, ALT, GGT), sex-steroids:(DHEAS, free and total testosterone, sex hormone binding globulin, progesterone, estradiol); Body size and composition: (BMI, waist/hip ratio, DEXA, hepatic visceral fat via MRI), Whole body fat oxidation at rest and following glucose ingestion as measured with a metabolic cart; Physical activity/ diet:(accelerometer, 3-day physical activity recall questionnaire (3DPAR); Food frequency questionnaire).Questionnaires for presence of obstructive sleep apnea. Questionnaires for perceived mental strengths and difficulty (note there is no assessment of suicidality on this tool). Obstructive Sleep Apnea, to be assessed with an overnight sleep study via WatchPAT.

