samples are collected at frequent intervals per **Figure 10** for positional NMR isotopomer analysis by collaborator [name] at UT Southwestern. Analyses will include modeling metabolic flux utilizing custom designed software and endpoints will include rates of excess TCA cycling contributing to triglyceride synthesis and gluconeogenesis as shown in **Figure 8**. This will be followed by a OSTT (75-gram glucose and 25-gram fructose) with frequent sampling of glucose, insulin, C-peptide. Fasting insulin sensitivity will be calculated with HOMA-IR (fasting glucose\* fasting insulin/22.4). The Matsuda index will be used to estimate whole body post-prandial insulin sensitivity and indices of hepatic [Glucose0–30(AUC)/insulin0–30(AUC)] and muscle insulin sensitivity [dGlucose/dtime ÷ insulin] with calculations starting at the downslope of glucose concentration. Blood glucose will be measured at the 2 hour time point and >140 mg/dL is defined as impaired glucose tolerance. Rates of fasting gluconeogenesis will be measured from the tracer incorporation of deuterated water into glucose, with samples analyzed with GCMS by collaborator [name], as previously described in youth. **Metabolomics:** Targeted amino acid and amino acid breakdown product metabolomics profiles will be measured by the University of Colorado metabolomics core on fasting and 120 minute post glucose drink samples (<https://www.dalessandrolab.com/home>).

Study Calendar	Screen	Phase I		Phase 2	
	Visit 1	Visit 2 –MRI	Visit 3 – Overnight	Visit 4 –MRI	Visit 5 – Overnight
Consenting and Eligibility Assessment	X				
History & Physical	X				
Intravenous Blood Draw	X		X		X
Fibroscan -Liver ultrasound	X		X		X
Randomization- Placebo vs EAA	X				
Crossover- Placebo vs EAA			X		
Accelerometer teaching	X				
Gut Bacteria Collection			X		X
Urine Pregnancy Test			X		X
Questionnaires- SEARCH Food frequency, Activity 3DPA, Strengths and Difficulties and Sleep assessments			X		X
DEXA Scan (located in Leprino building)			X		X
Oral Glycerol Tracer with D 2 O			X		X
Oral Sugar Tolerance Test (OSTT)			X		X
WatchPAT sleep study			X		X
Metabolic Cart			X		X
EndoPat and Dynapulse		X		X	
MRI of abdomen and liver		X		X	
P MRS of Liver		X		X	
Total Time of visit (approximately)	2 Hours	2 Hours	22 Hours	2 Hours	22 Hours

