Aim 2: We expect that insulin sensitivity will improve following EAA and that the glucose concentration at 2 hours of the OSTT will decrease. The reproducibility of glucose measurement from an OSTT in any individual is only 75%, however, this is when the effects of exercise, diet, sleep and menstrual cycle are not controlled. An alternate approach for assessing insulin sensitivity would be a hyperinsulinemic euglycemic clamp, for which we have extensive experience. We have not elected to use this as it is not physiologic and does not allow for isotopomer assessments. We expect to measure hepatic metabolism with metabolomics and isotopomer analysis and to integrate these results with clinical outcomes. We hypothesize that those with worse HS will have increased futile TCA cycling and increase BCAA which will improve with improved insulin sensitivity and decreases in liver fat after EAA. If our hypotheses are incorrect, the data may suggest additional mechanistic pathways unique to PCOS. Interpretation of the resulting data requires extensive knowledge of biochemistry and I have the unique skills, time, institutional support, collaborators, and mentoring to be successful.

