## VII. Data Analysis Plan:

### Overall Project Statistical Plan:

Sample size analysis: Sample size is based on the power to detect a change in IHTG with treatment with EAA as compared to placebo (primary endpoint). Assuming a 2-sided  $\alpha=0.05$ , 20 participants provides 86% power to detect a change of 2.8% in IHTG, assuming a 3.9% standard deviation of change, which corresponds to a correlation of 0.8 between repeated measures. For Aim secondary measures, a 2 sample size of 20 gives 99% power to detect a change of 14.4 mg/dL in 2 hour OSTT glucose and 81% power to detect a change of 1.8 in HOMA-IR, assuming a standard deviation of 14.4 mg/dL and 2.7, respectively. Estimates of effect size and variability were conservatively estimated from the PI's extensive pilot data.

Analysis plan: No interim analyses are planned. Prior to the start of any formal analyses, unusual values that need to be queried, patterns of missing values, and whether their distributions are non-Gaussian will be identified. Demographic and clinical characteristics will be summarized with descriptive statistics. Analyses will follow the "intent-to-treat" principle so that study hypotheses are tested under realistic conditions in which not all participants adhere to the intervention. For the primary outcome, we will compare IHTG with and without EAA treatment using a paired t-test or a Wilcoxon signed rank test. Similar analyses will be used for secondary outcomes (2 hour OSTT glucose, HOMA-IR, metabolomics markers, proportion of direct/indirect glucose, EAA concentrations). Linear models will be used to identify the variables that are associated with change in IHTG, such 2 hour OSTT glucose, HOMA-IR, metabolomics markers, etc.

All measures will be adjusted for OSA status (yes/no) and/or severity of AHI.

Secondary outcomes include a Pearson correlation test of potentially related variables followed by targeted multiple regression to assess the relationship between hepatic fat and adipose IR, PEP, TCA, TG synthesis pathways.

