Metabolomics data: Differences in targeted metabolic concentrations will be compared between groups, after appropriate cleaning of the data, as performed by the processing site. Changes in metabolites over time will be compared between groups, to determine the times that demonstrate the largest differences. Results will also be compared to isotopomer results, to see if a metabolomics endpoint can yield similar information to the isotopomer analysis.

Gut Microbiota: The microbiota profile is entirely exploratory, and will be related to status of hepatic steatosis and 2 hour glucose status of impaired glucose tolerance or not.

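### The exploratory gut microbiota analysis uses 2-hour glucose only as impaired or not, which discards about a third of the information if roughly half the girls exceed 140 mg/dL

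*Combined protocol and SAP*

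**What the plan says.** Section VII, under Gut Microbiota, states that the profile "will be related to status of hepatic steatosis and 2 hour glucose status of impaired glucose tolerance or not". It introduces this with "The microbiota profile is entirely exploratory". Section III.A nevertheless names the profile in its list of secondary outcome measures: "Targeted glucose and fat metabolism metabolomics, and untargeted exploratory analysis, gut microbiota profile".

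The cut-point is in Section III.C, Aim 2: "Blood glucose will be measured at the 2 hour time point and >140 mg/dL is defined as impaired glucose tolerance". The numerical value is therefore available for every girl who has the sugar tolerance test.

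Elsewhere Section VII keeps that value on its full scale. The sample-size paragraph powers a mean change in mg/dL, and the analysis plan, after naming a paired t-test or signed rank test for the primary outcome, says "Similar analyses will be used for secondary outcomes (2 hour OSTT glucose, HOMA-IR, metabolomics markers". No section plans microbiota against glucose in mg/dL.

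This point concerns only the glucose grouping, not the hepatic steatosis status named in the same sentence.

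**The concern.** A girl at 141 mg/dL and a girl at 200 mg/dL are treated as identical, while girls at 139 and 141 mg/dL are treated as different. In a study of 20 completers, a two-group comparison uses the glucose data less efficiently than a correlation or regression on the measured value. A hypothesis-generating analysis of this size needs whatever sensitivity the data offer. At stake is a missed lead on microbiota and glycaemia. No primary result, and neither of the two specific aims, depends on it.

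**Working it through.** **Inputs from the document.** 20 completers (Section III.B). Two-sided alpha of 0.05 (Section VII, used there for the powered endpoints). Cut at 140 mg/dL (Section III.C, Aim 2). Share above the cut about 50%: Table 2 gives 50% for 38 girls with PCOS, and the text beneath it says "nearly half of girls had impaired glucose tolerance".

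**Input that the document does not give.** The true correlation between a microbiota measure and 2-hour glucose. I assume a range of 0.2 to 0.8.

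**Step 1: the plan's own power figures.** For a paired t-test with n = 20, the noncentrality is (change / SD) × √20.

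- IHTG: 2.8/3.9 × 4.472 = 3.21, power 86.1% (stated 86%).
- 2-hour glucose: 14.4/14.4 × 4.472 = 4.47, power 98.9% (stated 99%).
- HOMA-IR: 1.8/2.7 × 4.472 = 2.98, power 80.7% (stated 81%).

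All three reproduce. None concerns the microbiota.

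**Step 2: information kept by the cut.** For a normal variable cut so that a share p lies above the threshold c, the asymptotic efficiency relative to the full scale is φ(c)² / [p(1 − p)].

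- p = 0.50: 0.3989² / 0.25 = 0.637, and 20 × 0.637 = 12.7 girls.
- p = 0.35 (or 0.65): 0.603, or 12.1 girls.
- p = 0.25: 0.539, or 10.8 girls.
- p = 0.20: 0.490, or 9.8 girls.

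At an even split the loss is 1 − 0.637 = 0.363, roughly a third.

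**Step 3: what that means for power.** Simulation with 40,000 runs per cell: bivariate normal data, n = 20, one observation per girl, two-sided 5%, Pearson test on the full scale against the two-group test after a cut at p = 0.50. Losses are taken from unrounded values.

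| Assumed true correlation | Power, mg/dL | Power, cut | Loss (points) |
|---|---|---|---|
| 0.2 | 13.4% | 9.9% | 3.6 |
| 0.3 | 25.2% | 17.3% | 7.9 |
| 0.4 | 43.2% | 28.2% | 14.9 |
| 0.5 | 64.4% | 43.6% | 20.9 |
| 0.6 | 83.4% | 61.1% | 22.3 |
| 0.7 | 95.5% | 79.4% | 16.1 |
| 0.8 | 99.6% | 93.5% | 6.0 |

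Over the same correlations, the loss is about 3 to 25 points if 35% or 65% exceed the cut, 4 to 32 if 25% do, and 5 to 37 if 20% do.

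**Step 4: does noise in glucose add to the loss?** If measured glucose has reliability λ, its correlation with the microbiota measure falls from ρ to ρ√λ on the full scale. Cutting the measured value at its median multiplies that by √0.637 = 0.80, giving 0.80 × ρ√λ. The ratio of the two is 0.80 whatever λ is. Under this model, noise weakens both analyses by the same factor and adds no loss specific to the cut.

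**The case against.** The strongest reply is that nothing stated is wrong. The plan labels the analysis entirely exploratory and gives it no test, alpha, effect size or power. The 5% benchmark in the working is mine. The 140 mg/dL category is also prespecified and used consistently, so it is not a cut chosen from the data, and describing the microbiota by impaired-tolerance status is a legitimate question. This stands and limits the severity. It does not explain why the measured value should go unused.

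The model is also simpler than the plan. The Gut Bacteria Collection text describes sequencing with phylogenetic and taxon-based comparison of communities, whereas the simulation has one normal summary, such as a diversity index. The point figures do not carry over to a multi-taxon analysis.

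The even split is an extrapolation. Table 2 covers girls with PCOS generally, while this trial enrols only those with hepatic steatosis, so the true share above 140 mg/dL is unknown.

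It could be argued that a continuous analysis is already permitted, because Section VII mentions Pearson correlations among secondary outcomes. That sentence goes on to hepatic fat, adipose insulin resistance and metabolic pathways, and does not mention the microbiota. The microbiota paragraph has its own, binary, specification.

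Finally, a reader might take Section IV's statement, "The reproducibility of glucose measurement from an OSTT in any individual is only 75" per cent, to mean that misclassification around 140 mg/dL costs further power beyond the table. Step 4 shows that this does not follow. The 75% figure also refers to uncontrolled exercise, diet, sleep and cycle, several of which the plan controls at least in part.

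**Conclusion.** The point holds as a minor, inexpensive improvement. The plan reduces a measured variable to two groups in one analysis, without a stated reason, while keeping its scale elsewhere. With a near-even split and approximate normality, about 36% of the information is lost.

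In power terms, the cost is about 4 to 22 points at an even split over assumed correlations of 0.2 to 0.8, for a single microbiota summary with one observation per girl. A reader might infer a flat loss of 15 to 22 points. That range needs a true correlation of about 0.4 to 0.7, and the documents supply none. At 0.2 to 0.3 the loss is only 4 to 8 points, and power is about 25% or less even on the full scale, so the change would not rescue the analysis. Nor should a reader infer that a stated operating characteristic is in error: the three stated powers reproduce, and none is claimed here.

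**What to change.** In Section VII, Gut Microbiota, replace the impaired-or-not grouping with 2-hour glucose from the sugar tolerance test, in mg/dL, as a continuous variable. Use Spearman correlation or a linear model for diversity and individual taxa, and enter glucose as a continuous covariate in community-level comparisons. Keep the 140 mg/dL split as a descriptive summary.

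State that each stool sample is paired with the glucose from the same treatment period. The Study Calendar marks stool collection at Visits 3 and 5, and the Visit 5 section refers back to Visit 3, but the Gut Bacteria Collection text and Section D.17 name only Visit 3. The same edit should settle the number of samples. If there are two per girl, the model must allow for repeated measures.

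The cost is a sentence or two in the analysis plan, with no new data, visits or participants. It should be made before analysis so that the choice of scale is prespecified. The small downside is that a continuous association is less directly clinical than impaired versus not impaired; the retained descriptive split covers that.

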## **VIII. Summarize Knowledge to be Gained:**

**Overall Expected Results:** We anticipate that we will determine which specific areas of hepatic metabolism are upregulated in girls with hepatic steatosis and can these be changed with EAA supplementation. This data would then provide the background evidence for future larger therapeutic trials. We will also continue to refine the isotopomer protocol with extension into fasting.

**Significance:** Recent evidence in adults with PCOS indicates that 60-70% have NAFLD. Our data shows that > 45% of obese girls with PCOS have NAFLD, likely an underestimate due to exclusion criteria of T2D and weight >250 lbs in the previous protocols. The majority of NAFLD studies have focused on males, and none have been performed in multi-race cohorts of girls with PCOS, despite this high prevalence. NAFLD has been described as the primary driver of worsening metabolic syndrome and CVD in obesity across populations, and can progress to cirrhosis and liver failure. Thus, understanding the hepatic metabolism associated with NAFLD is critical to designing strategies to improve the long-term health of these girls and reduce their risk of T2D, CVD and liver failure. Further, we will be testing a well-tolerated oral nutritional supplement.

